#### 4.4. Inclusion and Exclusion Criteria

**Inclusion Criteria:**

- Patients under 18 years of age.
- Post-cardiac surgery patients in the CICU of RSUPN.
- Patients at high risk of extubation failure (e.g., young age, open sternotomy, mechanical ventilation >48 hours).
- Patients who pass the extubation readiness test and spontaneous breathing trial.

**Exclusion Criteria:**

- Diaphragmatic paralysis.
- Decreased consciousness.
- Neuromuscular disease.
- Pneumothorax without drainage.
- Airway obstruction.
- Patients with a tracheostomy.
- Unplanned extubation.
- Patient received PEEP >7 prior to extubation

#### **4.5. Sample Size Estimation**

The sample size calculation follows the formula for unpaired categorical analytical studies. Based on the literature, the extubation failure rate with HFNC is 17%, and the minimum significant difference in proportion is 25%. The estimated sample size for each group is 57 patients, with a total of 114 patients for both groups.

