## CHAPTER 1 Introduction

### 1.1. Background

Congenital heart disease (CHD) is a significant global health concern, with a prevalence of 0.8–1.2% of total live births. In developed countries, post-cardiac surgery mortality rates among pediatric patients tend to be low. However, data from Indonesia, particularly from [name] National General Hospital (RSCM), indicate a significant mortality rate. Over the past 3–5 years, the post-cardiac surgery mortality rate among pediatric patients at RSCM has been approximately 13.6%, primarily due to complications such as low cardiac output syndrome (LCOS), arrhythmias, multi-organ dysfunction, and extubation failure. The incidence of extubation failure in pediatric cardiac surgery patients ranges from 9.7% to 17.6%, often associated with airway, neurological, cardiac, diaphragmatic, and electrolyte-related factors. Patients experiencing repeated extubation failure have a higher risk of mortality compared to those who either do not experience it or fail extubation only once. Therefore, identifying effective solutions to mitigate the risk of extubation failure is of critical importance.

Non-invasive ventilation (NIV) and high-flow nasal cannula (HFNC) are commonly implemented in healthcare centers to reduce the incidence of extubation failure. However, the effectiveness of HFNC in minimizing extubation failure among high-risk pediatric cardiac surgery patients remains uncertain, particularly in Indonesia. At RSCM, the systematic and widespread use of HFNC in managing post-cardiac surgery pediatric patients requires further investigation to establish its efficacy. This study aims to address this gap by comparing extubation success rates between HFNC and NIV at RSCM.

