### **Comparison of the Effectiveness of HFNC and NIV**

Studies comparing HFNC and NIV in pediatric post-cardiac surgery patients have yielded mixed results. Some research supports HFNC as a more comfortable and easier-to-implement modality, particularly due to its less invasive nasal cannula interface compared to the masks used in NIV. Furthermore, HFNC is considered more user-friendly in non-ICU settings. Conversely, NIV has been utilized for a longer duration in intensive care settings and is known for providing stable positive pressure, which helps prevent alveolar collapse and improves gas exchange in patients with compromised pulmonary function.

[figure not shown]
A study by Zhou et al. (2024) found that HFNC significantly reduced reintubation risk (RR = 0.36,  $P < 0.00001$ ) and shortened ICU stay duration (MD = -4.75,  $P = 0.04$ ). Similarly, research by Elmitwalli et al. (2024) reported that HFNC decreased reintubation rates (RR = 0.45,  $P < 0.01$ ), mortality (RR = 0.31,  $P < 0.01$ ), as well as length of hospital stay (-8.76 days,  $P < 0.01$ ) and ICU stay (-4.63 days,  $P = 0.04$ ). However, compared to conventional oxygen therapy, no significant differences were observed in reintubation rates. A study by Kuitunen (2023) concluded that there was insufficient evidence to establish a definitive difference in reintubation rates and other clinical outcomes between different non-invasive ventilation strategies, due to high bias risk and limited study numbers.

The debate continues regarding which modality is more effective in reducing extubation failure and mortality. HFNC provides benefits for patients with moderate-to-severe respiratory failure risk, whereas NIV may be more suitable for patients with severe pulmonary conditions. Further research is required to determine the optimal post-extubation strategy for pediatric post-cardiac surgery patients.

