### 4.3. Population and Sample

The study population consists of **pediatric patients undergoing post-cardiac surgery** and receiving care in the **CICU at RSUPN Cipto Mangunkusumo, Jakarta**. The study sample will be selected based on predefined **inclusion and exclusion criteria**, with the total sample size determined using an appropriate statistical estimation formula. The sample size estimation will be calculated using the following formula:

$$n1 = n2 = \left( \frac{Z\alpha\sqrt{2PQ} + Z\beta\sqrt{P1Q1 + P2Q2}}{P1 - P2} \right)^2$$

Description:

n1 = n2 = Sample size

Za = Standard deviation for Type I error = 5% = 1,96

Zb = Standard deviation for Type II error = 20% = 0,84

P1 – P2 = Minimum significant difference in proportion = 0,25

P2 = Extubation failure rate with HFNC based on literature is 17% or equivalent to 0,17.

Q2 = 1 – 0,17 = 0,83

P1 = P2 + 0,25 = 0,17 + 0,25 = 0,42

Q1 = 1 – P1 = 1 – 0,42 = 0,58

P = (P1 + P2)/2 = (0,42 + 0,17)/2 = 0,295

Q = 1 – P = 1 – 0,295 = 0,705

$$n1 = n2 = \left( \frac{1,96\sqrt{2x0,295x0,705} + 0,84\sqrt{0,42x0,58 + 0,17x0,83}}{0,42 - 0,17} \right)^2 = 51$$

Meanwhile, when estimating the sample size based on the outcome of reintubation rate reduction, the calculation is as follows

$$n1 = n2 = \left( \frac{Z\alpha\sqrt{2PQ} + Z\beta\sqrt{P1Q1 + P2Q2}}{P1 - P2} \right)^2$$

Description:

P1 (HFNC) = 0.37 (HFNC reintubation rate)

P2 (NIV) = 0.15 (NIV reintubation rate)

P1 - P2 = 0.25 (Difference to be detected)

Q1 = 1 - P1 = 1 - 0.37 = 0.63

Q2 = 1 - P2 = 1 - 0.15 = 0.88

P = (P1 + P2) / 2 = (0.37 + 0.17) / 2 = 0.245

Q = 1 - P = 1 - 0.245 = 0.755

$$n1 = n2 = \left( \frac{1,96\sqrt{2x0,245x0,755} + 0,84\sqrt{(0,37x0,63) + (0,12x0,88)}}{0,25} \right)^2$$

= 45.22 ~ 46 subjects

Similarly, when estimating the sample size based on the outcome of mortality reduction, the calculation is as follows:

$$n1 = n2 = \left( \frac{Z\alpha\sqrt{2PQ} + Z\beta\sqrt{P1Q1 + P2Q2}}{P1 - P2} \right)^2$$

Description:

P1 (HFNC) = 0.1 (Mortality rate with HFNC)

P2 (NIV) = 0.35 (Mortality rate with NIV)

P1 - P2 = 0.25 (The difference to be detected)

Q1 = 1 - P1 = 1 - 0.1 = 0.9

$$Q2 = 1 - P2 = 1 - 0,35 = 0,65$$

$$P = (P1 + P2) / 2 = (0,1 + 0,33) / 2 = 0,225$$

$$Q = 1 - P = 1 - 0,225 = 0,77$$

$$n1 = n2 = \left( \frac{1,96\sqrt{2 \times 0,225 \times 0,775} + 0,84\sqrt{(0,1 \times 0,9) + (0,35 \times 0,65)}}{0,25} \right)^2$$
$$= 42,54 \sim 43 \text{ subjek}$$

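### The sample size rests on a 42% NIV failure rate that the protocol does not source and that its own second calculation contradicts; the 80% power depends on that rate

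*Protocol*

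**What the plan says.** Section 4.3 (Population and Sample) uses the two-proportion formula with "Za = Standard deviation for Type I error = 5% = 1,96" and "Zb = Standard deviation for Type II error = 20% = 0,84". The HFNC rate is entered as "P2 = Extubation failure rate with HFNC based on literature is 17% or equivalent to 0,17". The comparator rate is not entered from a source; it is built up as "P1 = P2 + 0,25 = 0,17 + 0,25 = 0,42", where the added term is "P1 – P2 = Minimum significant difference in proportion = 0,25". The result is 51 per group, raised to 57 (114 in total) for 10% loss. Section 4.5 repeats the 17% and says "the minimum significant difference in proportion is 25" per cent.

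Three other places bear on these inputs:

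- **Incidence.** Section 1.1 says "The incidence of extubation failure in pediatric cardiac surgery patients ranges from 9.7% to 17.6" per cent. Chapter II repeats the range. No other incidence of extubation failure is quoted.
- **Relative effect.** The comparison section of Chapter II reports one meta-analysis in which "HFNC significantly reduced reintubation risk (RR = 0.36" and a second with a relative risk of 0.45. It also cites a systematic review that found too little evidence to establish a difference.
- **Second calculation.** Section 4.3 then sizes on reintubation, with HFNC at 0.37 and NIV at 0.15. The difference is labelled 0.25, and 0.12 replaces 0.15 inside the formula. Table 1 defines extubation failure as reintubation within 72 hours.

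**The concern.** The power of the trial depends on the comparator rate, and that rate comes from adding the difference the trial would like to detect. It lies far above the only incidence the protocol reports. The next calculation in the same section gives NIV a rate about a third as high and makes HFNC the worse arm. If the two calculations concern the same event, they cannot both describe what the investigators expect.

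Calling 25 points the minimum significant difference also tells the reader that 57 per group is enough for the smallest difference of interest. That holds only if differences well below 25 points do not matter, which the protocol does not argue. The research question in section 1.3 is whether HFNC is as effective as NIV, and the proposal's summary expects comparable success rates. A non-significant result from a trial with little power could therefore be taken as support for that expectation.

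**Working it through.** **Inputs.** z = 1.96 and 0.84, HFNC 0.17, difference 0.25 (section 4.3); 51 and 57 per group (section 4.3); incidence 9.7% to 17.6% (section 1.1 and Chapter II); relative risks 0.36 and 0.45 (Chapter II). The 30% NIV rate below is my assumption, standing for a moderately enriched high-risk population.

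**1. The protocol's own figure.** P = (0.42 + 0.17)/2 = 0.295 and Q = 0.705.

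n = [(1.96·√(2·0.295·0.705) + 0.84·√(0.42·0.58 + 0.17·0.83)) / 0.25]² = [(1.2641 + 0.5210)/0.25]² = 50.98, so 51. It reproduces.

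**2. Power from the same formula, inverted.**

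Power = Φ{ (|P1 − P2|·√n − 1.96·√(2PQ)) / √(P1Q1 + P2Q2) }

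For 42% vs 17%: n = 51 gives (1.7854 − 1.2641)/0.6202 = 0.840, power 80%; n = 57 gives (1.8875 − 1.2641)/0.6202 = 1.005, power 84%.

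**3. Where 42% sits.** 0.42/0.176 = 2.4 times the top of the quoted range. The implied relative risk is 0.17/0.42 = 0.40, between the two cited values. Holding HFNC at 17%, those values imply NIV rates of 0.17/0.36 = 47% and 0.17/0.45 = 38%.

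**4. Power over the range, 57 per group, two-sided 5%.**

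| Anchor | Relative risk | NIV vs HFNC | Power |
|---|---|---|---|
| Protocol's pair | 0.40 | 42% vs 17% | 84% |
| HFNC 17% | 0.36 | 47% vs 17% | 94% |
| HFNC 17% | 0.45 | 38% vs 17% | 71% |
| NIV 30% (assumed) | 0.36 | 30% vs 10.8% | 73% |
| NIV 30% (assumed) | 0.45 | 30% vs 13.5% | 57% |
| NIV 17.6% | 0.36 | 17.6% vs 6.3% | 46% |
| NIV 17.6% | 0.45 | 17.6% vs 7.9% | 34% |
| NIV 9.7% | 0.36 | 9.7% vs 3.5% | 26% |
| NIV 9.7% | 0.45 | 9.7% vs 4.4% | 20% |

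Exact enumeration of the chi-square test gives 85% for the protocol's pair and 47% and 34% for the two rows at 17.6%, so the approximation is not driving the result.

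**5. The second calculation.** With 0.37 and 0.12 the formula gives 45.2, so 46, as printed. With the declared 0.15 the difference is 0.22, not 0.25, and the formula gives 61.1, so 62 per group, more than the 57 planned. The two sizing calculations compare as follows:

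| | NIV | HFNC | Worse arm |
|---|---|---|---|
| Extubation failure | 42% | 17% | NIV |
| Reintubation | 15% (0.12 in formula) | 37% | HFNC |

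**6. Expected precision.** With 17% in both arms and 57 per group, the 95% CI half-width for the risk difference is 1.96·√(2·0.17·0.83/57) = 0.138, about ±14 points.

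**The case against.** The strongest defence is that the quoted range is a general incidence after paediatric cardiac surgery, whereas section 4.4 admits only children at high risk of extubation failure. The only arm-specific failure rate that the protocol attributes to the literature is 17% on HFNC. With that rate held and the cited relative risks applied, NIV failure is 38% to 47%, which brackets 42%, and power at 57 per group is 71% to 94%. Pairing NIV with 17.6% or 9.7% pushes HFNC failure down to 3.5% to 7.9%, below the stated 17%.

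This stands as far as it goes, and it is why the range must show both anchors. It does not supply the missing justification. The protocol never makes the argument, gives no failure rate for high-risk children, and cites a review that found the evidence on relative effect inconclusive. At a relative risk of 0.45, the same argument still leaves power at 71%.

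A reader might infer that the design is impossible, because a fall of 25 points cannot start from 17.6% or less. The documents do not support that: the 25 points are added to the HFNC rate, so the design needs a high comparator rate, not a negative one. A reader might also infer that the 80% power does not exist, or that nothing in the document is compatible with 42%. Neither holds. The power is correct under its stated rates, and 17% combined with the cited relative risks reaches the same region.

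Rules for reporting a null result often belong in an analysis plan, which is not shown. No misreading has occurred, and the protocol contains no rule that would produce one. The case for a sentence here rests on the comparability wording of the research question.

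**Conclusion.** The concern holds as a fault in the assumption, not in the arithmetic. The comparator rate of 42% is unsourced, is 2.4 times the top of the only quoted incidence, and conflicts with the reintubation calculation in the same section in both level and direction. The power stated for the trial depends on it.

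With 57 per group, power runs from 94% down to 20% over rates that can be formed from the protocol's own figures, with 57% to 73% at an assumed intermediate NIV rate of 30%. The documents do not show where in this span the trial lies. All these figures assume a two-sided 5% test, the protocol's formula and 57 evaluable per group. With the planned 10% loss, 51 are evaluable and power is lower: 80% instead of 84% for the protocol's pair, and 42% and 31% instead of 46% and 34% at 17.6%.

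**What to change.** In sections 4.3 and 4.5:

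1. Replace the minimum-significant-difference label with a statement that 25 points is the difference assumed for sizing.
2. Reconcile the NIV and HFNC rates, and the direction of the difference, between the extubation-failure and reintubation calculations. Correct the 0.15/0.12 and 0.22/0.25 mismatches.
3. State that 51 evaluable per group gives 80% power, and 57 gives 84%, under 42% vs 17%, and that 42% is an assumption for a high-risk population. Cite a source if one exists.
4. Show the power over the full range in the table above, including the favourable rows.
5. State the expected precision (about ±14 points with 17% in both arms) and that a non-significant difference will not by itself be reported as comparability.

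The sample size need not change and no extra patients are needed. The cost is a rewrite of two sections and a less favourable stated power.

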#### **4.6. Sampling Method**

Sampling is conducted consecutively from pediatric post-cardiac surgery patients who meet the inclusion criteria during the study period in the CICU of RSUPN Cipto Mangunkusumo. Subjects meeting the inclusion and exclusion criteria will be randomized into two intervention groups: the High Flow Nasal Cannula (HFNC) group and the Non-Invasive Ventilation (NIV) group, using a simple randomization method. Block randomization was employed to ensure balanced allocation between the intervention and control groups. Subject assignment within each block was conducted randomly using statistical software (e.g., SPSS or Excel), with allocation concealed from investigators involved in data collection to minimize potential bias.

#### **4.7. Data Collection Technique**

[figure not shown]
Data is collected through clinical observation and measurement of patients' respiratory parameters before and after therapy. A blood sample of 0.5–1.0 mL is taken one hour before and after therapy. Monitoring is conducted by a trained medical team, and data on extubation failure, vital parameters, and patients' clinical conditions are continuously recorded during hospitalization.

#### **4.8. Data Analysis**

[figure not shown]
Data will be processed using statistical software and analyzed through univariate and multivariate analyses.

- Univariate analysis will be used to describe subject characteristics.
- Multivariate analysis using binary logistic regression will be performed to identify factors influencing extubation failure.

[figure not shown]
**4.9. The Research Flowchart includes input, process, output, and outcome components based on the achievement indicators.**

**Image 3. Research Flowchart**

**Image 4. NIV Group Procedure**

**Image 5. HFNC Group Procedure**

#### 4.10. Research Timeline

No	Action Plan	Month										
		1	2	3	4	5	6	7	8	9	10	11
1.	Preparation and Ethical Approval Submission	■	■									
2.	Patient Recruitment and Randomization			■	■	■						
3.	Intervention Implementation (HFNC and NIV)						■	■				
4.	Data Collection and Monitoring							■	■			
5.	Data Analysis and Report Writing									■	■	■

